- **Opioid risk knowledge:** Participant's awareness of common and critical opioid risks will be assessed using the ADE knowledge instrument, where participants use nominal responses to record which are possible when taking opioids or when opioids are in the home.^{7,8,124} These items were developed with established content and face validity and, together with risk perceptions, were found to have predictive validity.^{7,8}
- **Opioid risk perceptions:** Perceived seriousness of opioid risks (e.g., excessive sedation, misuse, addiction) will be assessed using a 6 point Likert scale where 0=Not serious to 5=Extremely serious.^{7,8,46} We have previously demonstrated predictive validity of these items toward situational and analgesic decisions.^{7,8,46} Perceived risk severity has been shown to predict intention and health behavior.⁸²
- **Analgesic self-efficacy:** Analgesic self-efficacy will be measured using a six item scale where participants will score their confidence to safely and effectively give and stop analgesics when managing their pain and other symptoms.¹²⁶⁻¹²⁸ Self-efficacy is the perceived confidence to perform specific behaviors to attain effective health outcomes.¹²⁹ Measures of medication self-efficacy mediate symptom management and health behavior and predict medication behavior and therapeutic change.¹³⁰
- **Opioid decision-making:** Situational decisional exercises will be modified to assess opioid use and potential misuse decision-making. We recently used similar decision-making scenarios to assess misuse intentions among 15-23 year olds, and demonstrated significant associations between risk understanding, past misuse behavior and misuse intentions.⁹ Four scenarios will assess participants' 1) willingness to misuse opioids either by taking higher doses (or more frequent dosing) of the personal prescription, 2) intention to misuse a previously prescribed opioid prescription for ongoing pain 3) intention to use a friend's

prescribed opioid for ongoing pain 4) pain and symptom relief when opioid-related adverse events are present.

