- **Surgical factors:** The procedure, prior injury, duration of surgery, all perioperative analgesics given and details of participant's prescription and analgesic instructions will be recorded from the medical record.

Study Procedures (SEE TABLE 1 BELOW)

Group assignment: Participants will be randomly assigned a priori by computer generated randomization to one of the three groups: the Control Group (i.e., Routine provider

pen/verbal analgesic instruction), the STOMP written feedback (intervention) Group: (i.e., Routine provider information plus the STOMP written feedback) or the enhanced STOMP Video Feedback (intervention) Group (i.e., Routine provider information plus the STOMP Video feedback).

All baseline and follow-up surveys are completed by the subjects using a Qualtrics survey link via their own smartphone or computer (or our iPad if completed in person) to ensure completeness and privacy. Subjects will enter only an assigned, unique ID number with no other identifying information. STOMP (either written or video groups) will be provided together with each decision exercise (built into the survey itself). The electronic survey includes appropriate logic and prompts to minimize the potential for missing items.

Subjects will be texted/emailed survey links on day 0 (day before or on surgery), day 7, day 14, 1 & 3 months after discharge. Table 1 depicts the study assessments completed at each timepoint. These will be automatically scheduled via our umich gmail system. On each of the survey days, we will also send a text SMS reminder to participants (automated using the same process as our parent study). Subjects can opt to complete surveys via email link (Qualtrics) or via paper/pen (returned via mail). No more than 1 additional text reminder for each will be sent to subjects who have not completed their follow-up surveys.

Sample Size Determination

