Our sample size is based on our recent findings that 26% of adolescents/young adults indicated a willingness to misuse a prescribed opioid for pain management. We need 426 participants (142/group) to detect a clinically important effect of the STOMP intervention on misuse intention (i.e., decrease to 13%; 95% confidence and 80% power). This sample will be more than sufficient to detect an expected mean difference in opioid misuse risk perception between either intervention group and the control (MD 0.56, SD 1.21; sample needed = 122) and to test for a modest effect of the interventions in a factorial design (estimated eta squared 0.14; sample needed = 147). To allow for 30% loss to follow-up and to account for missing data, we will recruit up to 600 participants.

Table 1. Sequence of study assessments

Measures	Time 0 Baseline (preop)	Time 0.1 (Immediately Post-Session)	Time 1 (7 days)	Time 2 (14 days)	Time 3 (1 month)	Time 4 (3 months)
Demographics	x					
Pain, Analgesic and Misuse History	x					
Pain relief Preference	x			x		
Opioid knowledge/ risk perceptions	x	x		x	x	x
Opioid misuse risk perceptions	x	x		x	x	x
Scenario (situational) decision-making	x			x	x	x
Analgesic self-efficacy	x	x				
Pain interference			x	x	x	x
Opioid left-over disposal				x	x	x

Analgesic use and ADEs			x	x	x	x
Perioperative data	x					
Analgesic refill data				x		

DATA ANALYSES

Generalized estimating equations (GEE) will be used to model both continuous (i.e., negative binomial and Gaussian) and binary outcomes (i.e., binomial) for each aim.^{151,152} All models will include both time-varying measures (e.g., opioid risk perceptions) and time-invariant covariates (e.g., sex, race, etc.) and will use either an independent or exchangeable correlation structure to correct for within subject correlations. Analyses will use Stata's (STATA/SE v.13; STATA Corp., College Station, TX) 'xtgee' option as appropriate. All hypotheses per our conceptual model (Figure 3) will be tested at the 0.05 alpha level. Standardized coefficients and adjusted odds ratios will be computed to determine the relative effect size for each of the key independent variables.

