Missing data: The use of electronic surveys with built-in prompts for incomplete items will reduce the potential for missing responses. Patients will be contacted by phone, text or email (per their preference) to promote ongoing recording of postoperative data and to reduce the potential for missing data and LTF. We have used similar procedures to successfully ensure complete data and minimize loss to follow-up.^{8,25,94,153}

Any remaining missing data on surveys (e.g., assist or PR-Pref) will be examined for randomness and we will impute only partial non-response (e.g., missing 1 to 2 items of PR-Pref or assist) using a horizontal (i.e., per individual) approach. Largely incomplete or total survey non-response will be examined for non-randomness and potential bias (e.g., missing DAST-10). These missing data will not be imputed, however, outcomes will be compared for persons with missing vs. complete data to determine selection bias. We have adjusted our sample size to account for the potential for missing data. We will use pairwise deletion to use the available, complete cases to test our hypotheses.

Aim 1: Using GEE, we will examine the association between the STOMP intervention and the outcomes (risk seriousness perception, and situational opioid decisions). It is hypothesized that, compared to controls, patients who receive the STOMP intervention will have 1) enhanced risk perceptions (continuous measure) and 2) improved opioid decisions (scenario-based). Hypotheses 1 and 2 will be tested using both main and interaction effect models. In the main effects models, STOMP group assignment is our binary independent variable of interest. Time by intervention interaction effect models will be used to examine whether the STOMP group has improved opioid risk perceptions and decisions at the follow-up assessments compared to the control group. It is expected that there will be no difference between the intervention group and control group at baseline. However, significant interaction effect terms should emerge for the intervention group at the follow-up assessments.

Anticipated Problems and Solutions:

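### Aim 1 GEEs: fitting follow-up waves adjusted for the Time 0 outcome would be at least as efficient as the planned Time 0-referenced tests; for H2 this depends on Time 0 answers preceding feedback

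*Combined protocol and SAP*

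**What the plan says.** The Aim 1 paragraph of Data Analyses states: "Hypotheses 1 and 2 will be tested using both main and interaction effect models". For the first kind of model it adds: "In the main effects models, STOMP group assignment is our binary independent variable of interest". For the second it says: "It is expected that there will be no difference between the intervention group and control group at baseline", with interaction terms expected to emerge at the follow-up assessments. Time 0 is therefore, by implication, an outcome wave in the interaction model. Nothing is said about Time 0 rows in the main-effects model.

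The opening paragraph of Data Analyses describes covariates by example only: time-varying measures such as opioid risk perceptions, and "time-invariant covariates (e.g., sex, race, etc".). The Time 0 value of the outcome is not among the examples.

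Sample Size Determination works with 142 per group for misuse intention (26% falling to 13%, 80% power). For risk perception it uses the "expected mean difference in opioid misuse risk perception between either intervention group and the control" (MD 0.56, SD 1.21).

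Table 1 schedules scenario decisions at Time 0 and Times 2, 3 and 4, and risk perceptions at Time 0, Time 0.1 and Times 2, 3 and 4. The H2 outcome comes from the scenarios: "Situational decisional exercises will be modified to assess opioid use and potential misuse decision-making". Study Procedures says: "STOMP (either written or video groups) will be provided together with each decision exercise (built into the survey itself"). It does not say whether the Time 0 answer is recorded before the feedback appears.

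**The concern.** Both planned tests can use the Time 0 measurement less well than the design allows. An interaction referenced to Time 0 estimates the full effect, but it subtracts a noisy baseline value. That costs precision unless the within-person correlation is high. A main-effects coefficient that includes Time 0 rows averages in a wave where no difference is expected, so it understates the effect. Using the Time 0 outcome as a covariate in a model for follow-up waves avoids both costs and needs only data that Table 1 already schedules.

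At stake is precision for H2, the outcome that sized the trial. For H1 power is not in doubt. The issue there is a smaller main-effects estimate if Time 0 rows are included, and some precision.

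**Working it through.** **Inputs.** From Sample Size Determination: 26% vs 13%, 142 per group, MD 0.56, SD 1.21. From Table 1: one Time 0 and three follow-up waves for scenarios, one Time 0 and four later waves for risk perceptions. Assumed: two-sided 0.05; within-person correlation ρ of 0.3, 0.5 or 0.7; 13% at every follow-up; no missing data; no time-varying covariates.

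**1. The plan's own figure.** n = (1.960 + 0.842)² × (0.26×0.74 + 0.13×0.87) / 0.13² = 7.849 × 0.3055 / 0.0169 = 141.9, so 142 per group. This is a single-time comparison of two groups.

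**2. Dilution if Time 0 rows enter the main-effects model.**
- Misuse intention: the STOMP average is (0.26 + 3×0.13)/4 = 0.1625, and 0.26 − 0.1625 = 0.0975. So 13 points become 9.75, and the odds ratio moves from 0.425 to 0.552.
- Risk perception: 0.56 × 4/5 = 0.448.

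**3. Efficiency for the same contrast** (equal variances, exchangeable ρ, in units of the outcome variance per person).
- Single visit: interaction 2(1−ρ); adjusted 1−ρ². The ratio is 2/(1+ρ), which is 1.54, 1.33 and 1.18 at ρ = 0.3, 0.5 and 0.7.
- Average of three follow-ups: interaction (1+2ρ)/3 + 1 − 2ρ; adjusted (1+2ρ)/3 − ρ². The difference is (1−ρ)², which is never negative.

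The ranking therefore does not depend on ρ. The size of the gain does.

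**4. Worked H2 example on the risk-difference scale** (142 vs 142, ρ = 0.5). The two variances are 0.1924 and 0.1131, and √(0.1924×0.1131) = 0.1475.
- Single-visit interaction: variance [0.1924 + (0.3055 − 0.1475)]/142, SE 0.0497; 0.13/0.0497 − 1.96 = 0.66; power 74%.
- Single visit, adjusted: variance about 0.75×0.3055/142, SE about 0.040; power about 90%.
- Main effect with Time 0 rows: control 0.1924×2.5/4 = 0.1203; STOMP [0.1924 + 3×0.1131 + 3×0.1475 + 3×0.1131]/16 = 0.0821; SE √(0.2024/142) = 0.0378; 0.0975/0.0378 − 1.96 = 0.62; power 73%.
- Main effect, follow-up rows only: SE √(0.3055×0.667/142) = 0.0379; power 93%.

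Across ρ = 0.3/0.5/0.7 the same method gives 60/74/92% (interaction), 84/90/97% (adjusted), 84/73/64% (main effect with Time 0 rows) and 97/93/88% (follow-up rows only). The 0.7 column is approximate, because with 26% and 13% the correlation within a STOMP arm cannot exceed √0.425 = 0.65.

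**5. Power on the planned logit scale**, by simulated GEE (latent normal model, independence working structure, robust standard errors, 4000 replicates, Monte Carlo SE at most 0.8 points), in % at ρ = 0.3/0.5/0.7:

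| H2 test | One arm, 142 vs 142 | Arms pooled, 284 vs 142 |
|---|---|---|
| Main effect with Time 0 rows | 86.6 / 73.8 / 65.2 | 93.2 / 86.6 / 77.3 |
| Main effect, follow-up rows only | 97.5 / 93.1 / 87.5 | 99.4 / 97.8 / 95.5 |
| Interaction, single visit | 68.3 / 81.9 / 94.1 | 82.3 / 92.8 / 98.7 |
| Interaction, joint 3 df | 73.7 / 86.7 / 96.5 | 88.3 / 96.1 / 99.6 |
| Time 0-adjusted, single visit | 83.8 / 88.8 / 96.1 | 91.6 / 96.1 / 99.1 |

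The single-visit gain from adjustment over the interaction is about 15, 7 and 2 points for one arm, and about 9, 3 and under 1 point pooled.

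**6. H1** (142 per group). Power = Φ(d / [1.21√(2v/142)] − 1.96).
- Main effect with Time 0 rows: d = 0.448, v = (1+4ρ)/5, giving 99.7/98.1/94.7%.
- Single-visit interaction: d = 0.56, v = 2(1−ρ), giving 90.9/97.4/99.9%.
- Single visit, adjusted: d = 0.56, v = 1−ρ², giving 98.3/99.5/over 99.9%.

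**The case against.** A time-by-group interaction is a standard and valid analysis, and adjustment for the Time 0 outcome is unspecified rather than excluded. The binary STOMP variable reads most naturally as both arms pooled against control. On that reading the single-visit interaction exceeds 80% at every ρ tried on the logit scale, and the gain is modest. The main effect with Time 0 rows falls below 80% only at ρ = 0.7, and the plan never says those rows are included. All of this stands, and it limits the size of the point. It does not change the ranking of the methods.

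The calculations also simplify the plan. They omit the time-varying covariates that Data Analyses says every model will include, and they assume a constant effect. If the effect faded (13%, 20%, 26%), a separate simulation of one arm against control at correlations of about 0.18/0.39/0.63 gives a joint interaction test 54.7/69.4/87.9% power, against 51.6/50.8/55.3% for the averaged adjusted test. Like for like, adjustment still wins: the adjusted joint test has 68.9/78.3/90.7%. The advantage therefore holds for the same contrast only, which is one reason to name that contrast.

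A reader might infer that the Time 0 scenario answers are already altered by feedback. The documents do not show this. Table 1 labels Time 0 as a preoperative baseline separate from Time 0.1, feedback ordinarily follows an answer, and the plan expects no baseline difference. Only the order within the survey is unstated. It needs checking because an affected Time 0 answer would make both the interaction and the adjustment remove part of the effect.

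**Conclusion.** The point holds as a matter of efficiency. For the same contrast, follow-up waves adjusted for the Time 0 outcome are never less efficient than the interaction referenced to Time 0, and they avoid the possible dilution of the main effect. For H2 this is conditional on Time 0 answers preceding feedback. The size of the gain rests on an assumed ρ, 13% at every follow-up, no missing data and no time-varying covariates. It is largest for one arm at low ρ and small for pooled arms at moderate or high ρ. For H1, adjustment only improves precision.

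A reader might infer that the trial is underpowered for H2 as planned. The documents do not support that. Power below 80% appears only under particular unstated choices: Time 0 rows in the main effect for one arm at ρ of 0.5 or more, or pooled at 0.7; and, on the logit scale, a single-visit or joint 3-df interaction for one arm at ρ = 0.3. On the risk-difference scale the single-visit interaction is also below 80% for one arm at ρ = 0.5 (74%) and pooled at 0.3 (71%), as is the averaged interaction for one arm at 0.3 (75%). The unnamed contrast and the unstated handling of Time 0 rows are missing detail, not errors in themselves.

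**What to change.** Fit the Aim 1 GEEs to post-baseline waves only: scenarios at Times 2, 3 and 4, and risk perceptions at Times 0.1, 2, 3 and 4. Include arm, time, arm-by-time and the Time 0 outcome as a covariate, with robust variance. Name one primary contrast per hypothesis: one visit or the follow-up average, and each STOMP arm or both pooled against control.

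For H1, Time 0 is listed separately from the post-session measure, so adjustment is straightforward. For H2, confirm from the survey build that the Time 0 scenario answer is stored before any STOMP feedback. If it is not, use the follow-up-only comparison without that covariate, and do not test H2 by an interaction referenced to Time 0.

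The cost is SAP wording and one check of survey order, with no new visits or participants. There are two small downsides. The adjusted odds ratio becomes conditional (about 0.39/0.32/0.20 at ρ = 0.3/0.5/0.7, against a marginal 0.43). Reporting a standardised risk difference resolves this at no meaningful cost in power (85/89/96% against 84/89/96%, one arm, single visit). In addition, because the Missing data paragraph says of survey non-response that "These missing data will not be imputed", the SAP needs a stated rule for participants with no Time 0 answer.

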Our current research (R01DA044245) examines the ability of our interactive Scenario Tailored Opioid Messaging Program (STOMP) to shift these modifiable factors in a way that will improve parental opioid decision making and handling while simultaneously ensuring good pain management of their children. This intervention, thus, provides an innovative, balanced approach to address both the primary prevention of opioid-related adverse outcomes and effective pain management. Relevant to this supplement, we will modify STOMP messages and test their impact on opioid risk perceptions and risky decision-making among older adolescents and emerging adults who make most if not all analgesic treatment decisions for themselves.

Supplemental funding via PA-18-591 will enable us to expand the target population of our current project to include older adolescents and emerging adults who are prescribed opioids for an acute pain condition and who are among those at highest risk for misuse. Specifically, funding will allow us to modify our STOMP messages to address the risks of opioid misuse and personal strategies to manage symptoms, and compare the effect of these STOMP messages to routine opioid analgesic consent information. These objectives fall within the scope of our currently funded project, but effectively expand our target enrollment to address the high priority need for primary prevention among youth. Thus, with supplemental funding, we aim to test the following hypothesis:

- 1) Examine whether modified STOMP messages will improve opioid risk understanding, enhance misuse risk perceptions, improve analgesic self-efficacy, and opioid decision-making among older adolescents and emerging adults (ages 15-24) who are prescribed opioids for post-procedure pain management. We hypothesize that older adolescents and young adults who are randomized to the intervention (versus routine opioid information/consent) will exhibit; **(H1)** Greater and sustained understanding of the potential risks of opioid misuse **(H2)** Decreased intentions to medically or non-medically misuse opioids for personal use, or share (divert) personal prescriptions with others.

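### H1 claims a sustained effect, but nothing keeps the immediate post-session reading out of its main-effects test or makes the conclusion rest on later visits

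*Combined protocol and SAP*

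**What the plan says.** Specific Aims, aim 1, states H1 as "Greater and sustained understanding of the potential risks of opioid misuse". In Data Analyses, Aim 1, the outcomes are perceived seriousness of risk and scenario decisions, and "Hypotheses 1 and 2 will be tested using both main and interaction effect models". The main-effects GEE carries one binary STOMP term. The time-by-intervention models are meant to show whether STOMP is better at the follow-up assessments, with no group difference expected at baseline.

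Table 1 has a column headed "Time 0.1 (Immediately Post-Session". Both risk-perception measures are marked there and at Time 0, 14 days, 1 month and 3 months. Scenario decisions are marked at Time 0, 14 days, 1 month and 3 months only.

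All hypotheses "will be tested at the 0.05 alpha level", with an independent or exchangeable working correlation. Unreturned surveys are not imputed. The plan does not say which model decides H1, whether Time 0.1 is a follow-up assessment, which rows enter the main-effects model, or what result counts as sustained.

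**The concern.** One coefficient averaged over visits cannot separate a lasting shift from one seen only straight after the message. For risk perceptions, one of the four post-baseline readings is the immediate one. It is also likely to be the best attended, because it belongs to the preoperative session while later surveys lose people and are not imputed. A brief shift can therefore give a significant STOMP coefficient, and a fading effect gives an average larger than what remains after surgery.

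At stake is the word *sustained*. With no stated rule, a significant main effect could be offered as support for H1 although nothing is left at 14 days.

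**Working it through.** **The plan's own figures.** Sample Size Determination takes "26% of adolescents/young adults indicated a willingness to misuse a prescribed opioid for pain management" as the control rate and aims for "decrease to 13%; 95% confidence and 80% power"; "We need 426 participants (142/group" is its result. The unpooled formula gives (1.96 + 0.842)² × (0.26×0.74 + 0.13×0.87) / 0.13² = 7.849 × 0.3055 / 0.0169 = 141.9, so 142 per group reproduces. The same section gives "MD 0.56, SD 1.21; sample needed = 122" for risk perception and ties it to no visit. With 142 per group, a single reading has SE 1.21 × √(2/142) = 0.144 and about 97% power for 0.56.

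**Inputs.** From the plan: SD 1.21, 142 per group, up to 600 recruited, a 30% loss allowance, exchangeable correlation, alpha 0.05 (taken as two-sided). Assumed: 0.56 at Time 0.1 and zero afterwards; response of 100/90/80/70% at Time 0.1, 14 days, 1 month and 3 months; correlation ρ of 0.3 to 0.7; equal allocation, so 600 gives 200 controls against 400 in the merged STOMP arms.

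**Hand check, complete data.** The average over four readings is 0.56/4 = 0.14. Its SE is 1.21 × √[((1+3ρ)/4) × 2/142]. At ρ = 0.5 this is 0.1135, so z = 1.23 and the rejection probability is 23%.

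**With loss.** Generalised least squares with visit intercepts and one group term, V = 1.21²[(1−ρ)I + ρJ], summed over the dropout patterns (10% leave after each of Time 0.1, 14 days and 1 month; 70% complete). Rejection probability = Φ(β/SE − 1.96) + Φ(−β/SE − 1.96). Time 0.1 supplies 1/(1+0.9+0.8+0.7) = 1/3.4 = 29% of post-baseline rows, or 1/4.4 = 23% with Time 0 included. At ρ = 0.5 and 142 v 142, β = 0.185 and SE = 0.117, so z = 1.58 and the probability is 35%.

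| Rows in the model (shift at Time 0.1 only) | β | 142 v 142 | 200 v 400 |
|---|---|---|---|
| Time 0.1 and the three later visits | 0.18-0.19 | 32-40% | 53-65% |
| The same plus Time 0 | 0.13-0.14 | 19-27% | 32-46% |
| Three later visits only | 0 | 5% | 5% |

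**Sensitivity.** An independence structure gives 24-35% and 40-58% (post-baseline rows). Complete data, with 142 v 142 or 142 v 284 and Time 0 in or out, give 14-37%. Losing 30% from every survey from day 14 on (200 v 400, either structure, Time 0 in or out) gives 30-77%.

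**Fading effect.** With 0.56/0.28/0.14/0, ρ = 0.5 and 200 v 400, the pooled estimate is 0.29 with Time 0.1 and 0.16 over the three later visits.

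**Interaction model, shift at Time 0.1 only.** A joint 4-df test is significant in 94% to over 99% of complete-data trials, so it cannot separate brief from lasting. Read term by term (simulation, ρ = 0.5, 30% loss), the Time 0.1 term is significant about 100% of the time, each later term about 5%, and at least one later term 13%.

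**Is dropping Time 0.1 enough?** No. For 0.56 at 14 days only and zero later (response 90/80/70%), the pooled coefficient over the three later visits is 0.22-0.23. It is significant 39-48% of the time (142 v 142) or 63-75% (200 v 400).

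**The case against.** The strongest reply is that the plan already has the right tool. The interaction models are aimed at the follow-up assessments, and read visit by visit they can show whether an effect lasts. Data Analyses restates hypothesis 1 as enhanced perceptions, without the claim of persistence. A reader might infer that H1 rests on the main-effects model alone, or that the investigators intend to call a significant main effect sustained. The documents say neither. What remains is the missing decision rule.

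A reader might also take the 32-65% as inflated type I error. It is not: if the groups differ at Time 0.1, the average difference is not zero and rejecting is correct. The problem is one of interpretation.

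A third inference is that the missing Time 0.1 reading for decisions biases H1. It does not. It only means the H1 and H2 main effects average over different visits, and nowhere does the plan propose comparing the two coefficients.

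It is fair to add that the lower figures apply if Time 0 rows enter the model, which the text leaves open. In that case a fully lasting 0.56 is estimated at about 0.42, so pooling can understate as well as overstate. The 30% loss is an allowance; Specific Aims reports current loss below 15%. The direction survives all of this, since even complete data give 14-37%.

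**Conclusion.** The point holds as a gap in the decision rule that is cheap to close, not as an error in the test. H1 claims persistence, one of its two planned models averages in an immediate reading, and no sentence makes the conclusion depend on later visits. Under the stated assumptions a shift confined to Time 0.1 gives a significant main effect in 32-40% of trials (142 v 142) or 53-65% (200 v 400), and in 19-27% or 32-46% with Time 0 rows. The effect at Time 0.1, its absence later, the response by visit and the correlation are all assumed, because the documents do not give them. They set the size of the problem; whether it exists depends only on some shift at Time 0.1 entering the average.

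**What to change.** In Data Analyses, Aim 1:

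1. Fit the H1 main-effects GEE to the 14-day, 1-month and 3-month readings only, with the Time 0 value as a covariate. Report Time 0.1 separately as the immediate effect.
2. Base any statement that the effect is sustained on the visit-specific STOMP-versus-control contrasts from the interaction model at the later visits, including 3 months. Do not base it on a pooled coefficient, a joint interaction test or the Time 0.1 term. Say which contrasts must be significant: requiring each one needs no multiplicity adjustment, whereas accepting any one of them does (the 13% above).

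The cost is a few sentences and no new data. For a lasting 0.56 at ρ = 0.5 and 142 v 142, before baseline adjustment, the main-effect SE rises from 0.117 to 0.127 and power goes from 99.8% to 99.3%. Single-visit contrasts have less power. At 3 months with 70% response (142 × 0.7 = 99.4 per group), the unadjusted SE is 1.21 × √(2/99.4) = 0.172, so z = 3.26 and power is about 90%. Requiring several contrasts together lowers it further.
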